## **3.2 General study level definitions**

### **3.2.1 Analysis time points**

#### **3.2.1.1 Relative Day**

The relative day of a visit or an event with respect to the first administration of study medication (i.e. first patch application of Neupro) will be presented in subject data listings. Relative days will be calculated as follows:

- If the start (stop) date occurred prior to the first application of study medication, the relative day is calculated as start (stop) date minus date of first patch application. That means that in subject data listings, relative days based on this situation will be preceded by a '-'.
- If the start (stop) date occurred on or after the first application of study medication but prior to the last patch application, the relative day is calculated as start (stop) date minus date of first patch application + 1.
- If the start (stop) date occurred after the date of last patch application, the relative day is calculated as start (stop) date minus date of last patch application + 1. In subject data listings, relative days based on this situation will be preceded by a '+'.

Relative days will not be presented for partial or missing dates.

#### **3.2.1.2 End date of the Treatment Period**

The end date of the Treatment Period will be either the date of Visit 2 for subjects completing the Treatment Period, or the date of the Early Withdrawal for subjects who discontinued during the Treatment Period. If a subject does not have a Visit 2/EW, then the date of last known dose of study medication during the Treatment Period will define the end date of the Treatment Period.

### **3.2.2 Study periods**

The following study periods are defined for the classification by study period:

- Pretreatment Period: Prior to the date of first administration of study medication
- Treatment Period: On or after the date of first administration of study medication and prior to or on the date of last administration of study medication during the Treatment Period.

### **3.2.3 Mapping of assessments performed at Early Withdrawal Visit**

Efficacy and safety assessments at an Early Withdrawal Visit that correspond to a scheduled visit (Visit 2) will be summarized at the scheduled visit (Visit 2) if the assessment was scheduled to occur at that visit.

### **3.2.4 Rescreening**

Rescreening was not foreseen in the clinical study protocol. However one subject was rescreened. In this case, the initial screening is documented with a different subject number than the second screening and following visits of this same subject. The fact that a rescreened subject has 2 different subject numbers is not accounted for in the analysis, which means that the subject will be counted twice in the tables based on the Enrolled Set. This was decided to be acceptable due to the exploratory nature of this study, and will not impact the efficacy and safety analysis.

## **3.3 Definition of Baseline values**

Baseline values for efficacy and safety variables will be determined from the last available value on or before the day of the first patch application, unless otherwise noted for a specific type of data. In general, Baseline values will be the values collected at Visit 1.

## **3.4 Protocol deviations**

Important protocol deviations are deviations from the protocol which potentially could have a meaningful impact on study conduct or on the primary efficacy outcomes for an individual subject. The criteria for identifying important protocol deviations will be defined within the appropriate protocol-specific document. Important protocol deviations will be reviewed as part of the ongoing data cleaning process and data evaluation. All important deviations will be identified and documented prior to database lock to confirm exclusion from analysis sets.

## **3.5 Analysis sets**

Four analysis sets will be defined for this study: the Enrolled Set (ES), the Safety Set (SS), the Full Analysis Set (FAS), and the Per-Protocol Set (PPS).

### **3.5.1 Enrolled Set**

The ES will consist of all subjects who signed the Informed Consent form (ICF).

### **3.5.2 Safety Set**

The SS will consist of all subjects who received at least 1 dose of Neupro. A subject who received Neupro after screen failing is not considered as treated within the study and therefore not included in the SS. The SS will be used for the analysis of all demographic, disposition, and safety data.

### **3.5.3 Full Analysis Set**

The FAS will consist of all subjects who have at least 1 valid Baseline and at least 1 valid post Baseline efficacy measurement. That means, subjects in FAS have non-missing values at Visit 1

and at Visit 2 either for the UPDRS Part III Motor Score or for at least one Kinesia-ONE variable or for Neupro dose per 24h.

The FAS will be used for the analysis and presentation of the efficacy data. In the case of misallocation, subjects will primarily be analyzed according to Kinesia-360 application (yes/no). However, if applicable, sensitivity analysis will also be performed according to the randomized group.

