6.3 Withdrawal criteria

Subjects are free to withdraw from the study at any time, without prejudice to their continued care.

Subjects should be withdrawn from the study if any of the following events occur:

1. Subject develops an illness that would interfere with his/her continued participation.
2. Subject is noncompliant with the study procedures in the opinion of the Investigator.
3. Subject withdraws his/her consent.
4. The sponsor or a regulatory agency requests withdrawal of the subject.

For assessments to be performed in case of an Early Withdrawal, refer to [Table 5-1](#).

Investigators should attempt to obtain information on subjects in the case of withdrawal or discontinuation. For subjects considered as lost to follow up, the Investigator should make an effort (at least 1 phone call and 1 written message to the subject), and document his/her effort (date and summary of the phone call and copy of the written message in the source documents) to complete the final evaluation. All results of these evaluations and observations, together with a narrative description of the reason(s) for discontinuing the subject, including the date of discontinuation, must be recorded in the source documents. The electronic Case Report form (eCRF) must document the primary reason for withdrawal or discontinuation.

Investigators should contact the Medical Monitor, whenever possible, to discuss the withdrawal of a subject in advance.

For handling of dropouts, refer to [Section 12.6](#).

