## **2.2 Study variables**

### **2.2.1 Efficacy variables**

#### **2.2.1.1 Primary efficacy variables**

The primary efficacy variables of this study are:

- Change from Baseline (Visit 1/Week 1) to Visit 2 (Week 12/3 months after start of treatment with Neupro) in Unified Parkinson's Disease Rating Scale (UPDRS) Part III Motor Score
- Change from Baseline (Visit 1/Week 1) to Visit 2 (Week 12) in Kinesia-ONE variables:
  - finger tapping speed score
  - rest tremor score
  - averaged finger tapping speed and resting tremor scores
  - postural tremor score
  - finger tapping amplitude score
  - hand grasp speed score

- hand grasp amplitude score
- rapid alternating movement speed score
- rapid alternating amplitude score
- dyskinesia score
- kinetic tremor score
- rapid alternating movement rhythm score
- hand movements rhythm score
- finger tapping rhythm score
- average Kinesia-ONE score
- Neupro dose per 24h at Visit 2 (Week 12)
- Number of Neupro dose changes during the study (between Visit 1 and Visit 2)
- Discontinuation of treatment with Neupro during the course of the study

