## **4.2 Handling of dropouts or missing data**

Subjects who prematurely discontinue the study will be evaluated based on the data collected at the Withdrawal Visit. The Withdrawal Visit data will be used similar to Visit 2 data.

Adverse events with missing intensity will be assumed to be severe. Adverse events with missing relationship to study medication per the investigator will be assumed to be related.

For analyses of AEs and concomitant medication usage, a complete date must be established in order to correctly identify the AE or medication as occurring during treatment or not. For purposes of imputing missing components of partially-reported start and stop dates for AEs and for medication use, the algorithms listed below will be followed. Start and stop dates of AEs or concomitant medication will be displayed as reported in the subject data listings (i.e., no imputed values will be displayed in data listings).

- Missing start day, but month and year present: If the start of study medication occurred in the same month and year as the occurrence of the AE/concomitant medication, the start day of the event/concomitant medication will be assigned to the day of first application of study medication. Otherwise the start day will be set to the 1st day of the month.
- Missing start day and month, but year present: If the start of study medication occurred in the same year as the occurrence of the AE/concomitant medication, the start day and month will be assigned to the date of first application of study medication. Otherwise the start day and month will be set to January 1st.
- Missing end day, but month and year present: The end day will be set to the last day of the month.
- Missing end day and month, but year present: If the maximum of the subject's date of study termination or the date equivalent to 30 days after the subject's last application of study medication is the same year as the occurrence of the AE/Concomitant medication, then the end day and month will be set to the maximum of the date of study termination or the date equivalent to 30 days after last application of study medication. Otherwise the end day will be set to December 31st of the given year.

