## 8 EFFICACY ANALYSES

The efficacy analysis will be performed on the FAS and observed cases will be utilized. The PPS will be used for sensitivity analysis on selected efficacy variables.

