### **8.1.2 Primary analysis of the primary efficacy variables**

The efficacy variables, change from Baseline to Visit 2 (for all continuous efficacy variables not based on Kinesia-360, i.e. UPDRS Part III and Kinesia-ONE scores) will be analyzed utilizing an analysis of covariance (ANCOVA) with Baseline as a covariate, “center” as factor, and “group” as main factor. The 2 groups are the Experimental Group (EG) and the Control Group (CG).

The 2-sided null and alternative hypotheses are:

- Null hypothesis ( $H_0$ ): EG=CG
- Alternative hypothesis ( $H_a$ ): EG $\neq$ CG

EG: Represents the change from Baseline to Visit 2 for subjects in the Experimental Group.

CG: Represents the change from Baseline to Visit 2 for subjects in the Control Group.

The efficacy analysis will be performed on the FAS and observed cases will be utilized. The group effect will be estimated and presented with 95% 2-sided CIs and p-values.

The single items of UPDRS Part III and the sum score will be presented in listings, the sum score will be summarized by group, and the change from Baseline to Visit 2 in UPDRS Part III score will be analyzed using ANCOVA.

The change from Baseline to Visit 2 in each of the Kinesia-ONE scores will be analyzed using ANCOVA.

The Neupro dose per 24h at Visit 2 will be summarized by group, as well as the Neupro starting dose per 24h. Both assessments of Neupro dose will be related in a shift table by group. In addition, Neupro dose and Neupro dose change will be tabulated as continuous variable.

The number of Neupro dose changes after first administration until Visit 2 will be summarized by group.

The comparison of the rate of discontinuation of treatment with Neupro during the course of the study for the control group and the experimental group will be performed using logistic regression with factors for treatment and center.

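### The Neupro discontinuation comparison sits on the FAS, so a recorded stopper without Visit 2 or Early Withdrawal data can drop out; SAP 10.4.2 labels it a safety variable, which implies the SS

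*SAP*

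**What the plan says.** SAP 2.2.1.1 lists "Discontinuation of treatment with Neupro during the course of the study" among the primary efficacy variables; it serves the third primary objective (SAP 2.1.1). SAP 8.1.2 plans one test for it: "The comparison of the rate of discontinuation of treatment with Neupro during the course of the study" by logistic regression with treatment and center.

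On the analysis set, SAP 8 says: "The efficacy analysis will be performed on the FAS and observed cases will be utilized". SAP 8.1.2 repeats this, and SAP 3.5.3 gives the FAS the same role. Under 3.5.3 a subject must have a Visit 1 value plus a non-missing one "at Visit 2 either for the UPDRS Part III Motor Score or for at least one Kinesia-ONE variable or for Neupro dose per 24h". Stopping Neupro is not itself a qualifying value.

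Early Withdrawal data are carried to Visit 2. SAP 3.2.3: "Efficacy and safety assessments at an Early Withdrawal Visit that correspond to a scheduled visit (Visit 2) will be summarized at the scheduled visit". SAP 4.2: "Subjects who prematurely discontinue the study will be evaluated based on the data collected at the Withdrawal Visit".

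SAP 10.4.2 lists the same comparison as a safety variable and sends the reader to 8.1.2 for its description. SAP 10 opens by placing safety analyses, in general, on the SS as randomized. SAP 3.5.2 defines the SS by at least one dose of Neupro, leaving out anyone dosed only after screen failure, and sets no Visit 2 condition.

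**The concern.** Whether a subject is counted can depend on the outcome being counted. Many stoppers will cause no difficulty. Protocol 6.3 says "Subjects should be withdrawn from the study if any of the following events occur" and lists four criteria, none of which is stopping Neupro, so a stopper may simply attend Visit 2. The gap concerns a subject with a recorded stop who attends neither visit.

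The documents foresee that subject. Protocol 10.3.1 only encourages stoppers to attend Early Withdrawal, Protocol 6.3 has a lost-to-follow-up procedure, and SAP 3.2.1.2 has a fallback: "If a subject does not have a Visit 2/EW, then the date of last known dose of study medication during the Treatment Period" sets the end of the Treatment Period. A stop can also be known without a visit, from the concomitant medication pages (SAP 7), documented phone contacts (Protocol 8.3 and 8.4) or, in the Experimental Group only, the APP (Protocol 10.3.1).

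At stake are the estimated discontinuation rates and, if the loss differs by group, the odds ratio. The plan's stated purpose is to gain an impression of the device's effect, so these estimates are what the pilot delivers.

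**Working it through.** **Tracing the sets**

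| Question | Efficacy route (SAP 2.2.1.1, 8, 8.1.2, 3.5.3) | Safety route (SAP 10.4.2, 10, 3.5.2) |
|---|---|---|
| Set | FAS | SS |
| Visit 2 or Early Withdrawal value needed | Yes | No |
| Grouping if misallocated | Kinesia-360 use | As randomized |
| Recorded stopper seen at neither visit | Can be left out | Kept |

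The PPS is a subset of the FAS, and the as-randomized repeat in SAP 8.1.4 is also on the FAS. Neither brings an excluded stopper back.

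**Effect on rate and odds ratio**

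The documents give no discontinuation or attendance rates, so there is no plan figure to reproduce. The planned size is 20 per group (SAP 2.3); every other input below is assumed. Let p be the true stopping rate, m the share of stoppers and c the share of continuers with no Visit 2 or Early Withdrawal value; E and C denote the groups.

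- FAS rate = p(1−m) / [p(1−m) + (1−p)(1−c)]
- FAS OR = true OR × [(1−m_E)/(1−m_C)] × [(1−c_C)/(1−c_E)]
- 95% CI = exp(ln OR ± 1.96 × √(sum of the reciprocals of the four cells))

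If all continuers are seen (c = 0), the rates are understated, and the OR is unchanged when m_E = m_C.

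Crude ORs, Experimental versus Control, not adjusted for center, with all continuers seen:

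| True stoppers per group | Stoppers lost (E, C) | Analysed E vs C | OR (95% CI) |
|---|---|---|---|
| 6/20 | 0, 0 | 6/20 vs 6/20 | 1.00 (0.26 to 3.87) |
| 6/20 | 3, 3 | 3/17 vs 3/17 | 1.00 (0.17 to 5.83) |
| 6/20 | 0, 1 | 6/20 vs 5/19 | 1.20 (0.30 to 4.86) |
| 6/20 | 0, 2 | 6/20 vs 4/18 | 1.50 (0.35 to 6.50) |
| 6/20 | 2, 0 | 4/18 vs 6/20 | 0.67 (0.15 to 2.89) |
| 6/20 | 1, 4 | 5/19 vs 2/16 | 2.50 (0.41 to 15.1) |
| 6/20 | 4, 1 | 2/16 vs 5/19 | 0.40 (0.07 to 2.42) |
| 4/20 | 0, 2 | 4/20 vs 2/18 | 2.00 (0.32 to 12.5) |
| 4/20 | 2, 0 | 2/18 vs 4/20 | 0.50 (0.08 to 3.13) |

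Example, row (1, 4): (5/14)/(2/14) = 2.50. In row (3, 3) both rates fall from 30% to 3/17 = 17.6%.

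With a real difference, 4/20 versus 8/20, the OR is (4/16)/(8/12) = 0.375. Losing half the stoppers in Control only gives 4/20 versus 4/16, OR 0.75; in Experimental only, 2/18 versus 8/20, OR 0.19.

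If continuers are also lost, the rate need not be understated. With p = 0.30, m = 0.20 and c = 0.30: 0.24/(0.24 + 0.49) = 0.24/0.73 = 32.9%.

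**The case against.** **The set may not be the FAS.** In SAP 8.1.2 the FAS sentence follows the ANCOVA description, and the logistic regression comes later without naming a set. SAP 8.1.4 describes the primary analyses as ANCOVA with summary statistics, so its repeats may not cover the regression. Protocol 10.3.1 also calls the comparison a safety variable, and Protocol 12.4.1 puts all safety analyses on the SS. This supports choosing the SS, but it does not settle the text: SAP 3.5.3 and SAP 8 put efficacy analyses on the FAS without exception. SAP 10.4.2 never names the SS; that follows from its label and the opening of SAP 10.

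**Exclusion may not happen.** A Neupro dose alone admits a subject to the FAS, and a recorded stop could be coded as a Visit 2 dose of 0. No section says so, and SAP 8.1.1.3 does not say whether a stop counts as a decrease. Exclusion is therefore possible, not certain.

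**The group is small and differential loss is speculative.** Both points stand. The reminder calls, scheduled only in the Experimental Group, concern charging and wearing the devices, not attending Visit 2. Returning equipment at Visit 2, also only in that group, is the better reason to expect different attendance. Nothing in the documents supports the (1, 4) scenario in particular.

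**Other outputs show these subjects.** SAP 5.1 plans disposition tables on the SS and a Neupro discontinuation listing, and SAP 10.2 a table of TEAEs leading to discontinuation of study medication. With about 40 subjects, recorded stops could be counted by hand from the listing. None of these is the all-cause group comparison.

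**Conclusion.** The concern holds. The SAP gives two incompatible answers on the analysis set for a primary variable, and under the efficacy route a known stopper can be left out of the only all-cause comparison. The contradiction stands even if every stopper attends a visit.

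The size cannot be determined from the documents. If all continuers attend, the group rates are understated. The OR is then biased only if the share of unseen stoppers differs by group, in a direction that cannot be predicted. Every shifted OR in the 6/20 scenarios lies inside the full-data interval of 0.26 to 3.87, so the shift is small against sampling error at this size. SAP 4.5 declares all tests exploratory. The harm is a misdescribed primary variable in a pilot, not a false claim of significance. It should be fixed because the change is cheap and specific.

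**What to change.** - In SAP 8.1.2 and 10.4.2, name one set: run the discontinuation regression on the SS as randomized, the grouping SAP 10 already uses.
- Count every Neupro stop recorded on the CRF, by the same rule in both groups, whether or not Visit 2 or Early Withdrawal was attended.
- State how Neupro dose at Visit 2 is coded after a stop, and whether a stop counts as a dose change under SAP 8.1.1.3.
- State how subjects with unknown status are handled, and report their number by group. Bounding analyses (all stopped, all continuing) are optional.

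The cost is SAP wording: the SS is already defined and Neupro dosing is already on the CRF. The drawback is a status assumption for a few lost subjects. Amendment 1 already followed the Data Evaluation Meeting, so a change made after data review should be labelled post hoc.

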4.1.2 Other efficacy variables

- Change from Baseline to Visit 2 in the motor scores derived from the Kinesia-360 wearable technology by time (weekly/monthly) and by Neupro dose level (mg/24h) for the Experimental Group in:
 - average daily tremor score
 - average daily slowness score
 - average daily dyskinesia score
 - percent wear-time tremor detected
 - percent wear-time dyskinesia detected
 - percent wear-time user not moving
 - percent wear-time user was walking score
 - percent wear-time user active but not walking

- number of steps per hour while wearing device
- Change from Baseline to Visit 2 (Week 12) in the 39-Item Parkinson's Disease Questionnaire (PDQ-39) scores.
- Change from Baseline to Visit 2 (Week 12) in subject engagement questionnaire scores.

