12.1 Definition of analysis sets

Four analysis sets will be defined for this study: the Enrolled Set (ES), the Safety Set (SS), the Full Analysis Set (FAS), and the Per-Protocol Set (PPS).

The ES will consist of all subjects who signed the ICF.

The SS will consist of all subjects who received at least 1 dose of Neupro. The SS will be used for the analysis of all demographic, disposition, and safety data.

The FAS will consist of all subjects who have at least 1 valid Baseline and at least 1 valid post-Baseline efficacy measurement. The FAS will be used for the analysis and presentation of the efficacy data. In the case of misallocation, subjects will be primarily analyzed according to Kinesia-360 application (yes/no). However, if applicable, sensitivity analysis will also be performed according to the randomized group.

The PPS will consist of those subjects in the FAS who do not have any important protocol deviations that would have an impact on the efficacy variables. The PPS will be used for sensitivity analysis.

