### **2.2.1.2 Other efficacy variables**

Other efficacy variables are:

- Change from Baseline to Visit 2 in the motor scores derived from the Kinesia-360 wearable technology by time (weekly/monthly) for the Experimental Group in:
  - average daily tremor score
  - average daily slowness score
  - average daily dyskinesia score
  - percent wear-time tremor detected
  - percent wear-time dyskinesia detected
  - percent wear-time user not moving
  - percent wear-time user was walking score
  - percent wear-time user active but not walking
  - number of steps per hour while wearing device
- Number of days on Kinesia-360 device
- Change from Baseline to Visit 2 (Week 12) in the 39-Item Parkinson's Disease Questionnaire (PDQ-39) scores.
  - Change from Baseline to Visit 2 (Week 12) in subject engagement questionnaire scores.

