## **8.2 Analysis of other efficacy variables**

### **8.2.1 Kinesia-360 motor scores**

Kinesia-360-based efficacy data will be presented descriptively for the Experimental Group. Due to repeated measurements (during titration weekly and during maintenance), comparisons will be

performed by time point and also by dose, if applicable (dependent on number of subjects in respective dose groups). Optional time points might also be subject to analysis (dependent on number of subjects at respective time points or windows for time points).

Change from Baseline to Week 2, Week 3, Week 4, Week 7/8, and Week 11 in the motor scores derived from the Kinesia-360 wearable technology by Neupro dose level (mg/24h) for the Experimental Group will be summarized for following scores:

- average daily tremor score
- average daily slowness score
- average daily dyskinesia score
- percent wear-time tremor detected
- percent wear-time dyskinesia detected
- percent wear-time user not moving
- percent wear-time user was walking score
- percent wear-time user active but not walking
- number of steps per hour while wearing device

The average daily scores of tremor, slowness and dyskinesia will be derived from the 2-minutes interval data. Only those 2-minutes interval data records, when the device was not paused, will be considered. For each day, starting at 0:00 until 23:58, the available non-paused 2-minutes interval scores of tremor (and similarly for slowness and dyskinesia) will be selected and the arithmetic mean of these will be calculated which results in the average daily scores.

The percent wear-times and number of steps per hour will be derived from the daily Kinesia-360 data. Multiple records per day will be averaged and weighted by wear-time.

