These daily scores will be used to derive the scores per visit week. The daily scores will be averaged from 2 consecutive days of wearing in the respective assessment week. Assessments on study day 8 to 14 are eligible for Week 2 scores, assessments on study day 15 to 21 are eligible for Week 3 scores, assessments on study day 22 to 28 are eligible for Week 4 scores, assessments on study day 43 to 56 are eligible for Week 7/8 scores, and assessments on study day 71 to 77 are eligible for Week 11 assessments. The Week 7/8 is an artificially added Week, which considers the data collected on voluntary basis during that time interval, and therefore might have sparse data. If more than 2 consecutive assessments are available for Week 7/8, the latest 2 consecutive values will be considered. The same applies for the assessments in Week 2, Week 3, Week 4, and Week 11: If more than 2 consecutive assessments are available per week, the latest 2 consecutive values will be considered.

In addition, the maximum relative day of Kinesia-360 usage will be listed, and the number of days the subject used the Kinesia-360 device will be calculated by subject and summarized.

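### The SAP narrows the Full Analysis Set without declaring it, so Experimental Group subjects with Week 2-4 device recordings but no Visit 2 or Early Withdrawal value are left out of the Kinesia-360 summaries

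*SAP*

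**What the plan says.** Protocol 12.1: "The FAS will consist of all subjects who have at least 1 valid Baseline and at least 1 valid post-Baseline efficacy measurement". It names no visit and no instrument.

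SAP 3.5.3 opens with the same rule, then explains it as needing a Visit 1 value paired with one from "Visit 2 either for the UPDRS Part III Motor Score or for at least one Kinesia-ONE variable or for Neupro dose per 24h". No Kinesia-360 measure is on that list.

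Both documents class Kinesia-360 motor scores as other efficacy variables (protocol 4.1.2, SAP 2.2.1.2). The SAP adds "Number of days on Kinesia-360 device" to the same list.

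SAP section 8 begins: "The efficacy analysis will be performed on the FAS and observed cases will be utilized". Section 8.2.1 falls under that sentence and names no other set. It summarises "Change from Baseline to Week 2, Week 3, Week 4, Week 7/8, and Week 11 in the motor scores", and states that "the number of days the subject used the Kinesia-360 device will be calculated by subject and summarized".

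SAP 3.2.3 and 4.2 treat Early Withdrawal data as Visit 2 data. SAP 3.9, which lists changes to protocol-defined analyses, mentions only the extra Kinesia-ONE scores.

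**The concern.** The SAP presents its second sentence as a reading of the first, but the two rules do not select the same subjects. Kinesia-360 has its own Baseline (Days 2 and 3) and scheduled recordings in Weeks 2, 3, 4 and 11. A subject can therefore satisfy the protocol rule on device data alone and fail the SAP rule for want of an end-of-participation value.

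This matters for two outputs. The Kinesia-360 tables are the only repeated motor data between the two clinic visits, and the days-of-use summary is the plan's measure of how much the device was worn. Under the SAP rule, valid early recordings enter these outputs only if the subject later supplies a qualifying end value. For days of use, scheduled wear is lower for those who leave before Week 11, so the omission is selective on the schedule itself.

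**Working it through.** The documents give no loss rate, power, SD or dropout figure for this point (protocol 12.8 makes no formal sample size estimate), so there is no plan figure to reproduce. The check compares the two rules and then illustrates the size.

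**Who is affected**

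| Experimental Group subject with Days 2-3 and Week 2-4 recordings | Protocol 12.1 | SAP 3.5.3 |
|---|---|---|
| Qualifying value at Visit 2 | in | in |
| Leaves early, qualifying value at Early Withdrawal | in | in (mapped to Visit 2) |
| Neither visit; Neupro dose recorded elsewhere | in | not stated |
| Neither visit; no such dose record | in | out |

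The last row can occur. No visits are required from Week 2 until Visit 2 (protocol section 1). Device data reach the Investigator through the web portal after each day of measurement (protocol 8.3). Subjects who stop Neupro are encouraged, not obliged, to attend an Early Withdrawal Visit (protocol 10.3.1).

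The third row is open because SAP section 7 places Neupro dosing on the concomitant medication pages, and the Experimental Group is prompted for dose in the app at each device use (protocol Table 5-1, note c). The SAP does not say whether such a record can stand as a Visit 2 value.

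**Scheduled minimum days of use**

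Inputs: planned Experimental Group n = 20 (protocol 5.1.2); wear on Days 2-3 and on at least 2 days in each of Weeks 2, 3, 4 and 11 (protocol Table 5-1). The number lost, k = 1 to 4 (5-20%), is an assumption.

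- Completer: 2 + 4 × 2 = 10 days.
- Leaves after Week 4: 2 + 3 × 2 = 8 days.
- Leaves after Week 2: 2 + 1 × 2 = 4 days.

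Mean over all 20 = [10 × (20 − k) + d × k] / 20, where d is the leaver's days. The FAS mean is 10 throughout.

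| k | Kept in FAS | Mean, d = 8 | 10/mean − 1 | Mean, d = 4 | 10/mean − 1 |
|---|---|---|---|---|---|
| 1 | 19 | 9.9 | 1.0% | 9.7 | 3.1% |
| 2 | 18 | 9.8 | 2.0% | 9.4 | 6.4% |
| 3 | 17 | 9.7 | 3.1% | 9.1 | 9.9% |
| 4 | 16 | 9.6 | 4.2% | 8.8 | 13.6% |

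The d = 8 columns match the subject described here, who has recordings through Week 4. The d = 4 columns describe a different subject, with no Week 3 or Week 4 values to lose.

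**Chance that anyone is affected**

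P(at least one of 20) = 1 − (1 − r)^20. For assumed r = 5%, 10%, 15% and 20% this is 64%, 88%, 96% and 99%.

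**Motor scores**

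If leavers differ from the rest by δ SD, the mean shifts by (k/20) × δ. With assumed δ = 0.5 to 1, this runs from 0.05 × 0.5 = 0.025 SD (k = 1) to 0.20 × 1 = 0.20 SD (k = 4). The SE at n = 20 is 1/√20 = 0.224 SD, so the shift is about 0.1 to 0.9 SE. The documents support neither a sign nor a value for δ.

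**The case against.** The strongest reply is that the reach is narrow and the stakes are low. Much of it stands.

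- A reader might infer that every early leaver disappears from the Week 2-4 rows, or that those rows depend on a return to clinic at Week 12. The documents do not support this. The Early Withdrawal Visit repeats the Visit 2 assessments (protocol 8.6) and its data count as Visit 2, whenever it takes place. Protocol 6.3 also requires efforts to complete the final evaluation.
- Neupro dose alone can qualify a subject. If a dose recorded outside a visit counts, the affected group shrinks further. The SAP's silence limits any estimate and itself needs resolving.
- A reader might infer that early motor results will look too favourable. That requires leavers to have done worse, which nothing in the documents shows.
- The tables are descriptive and single-arm, in a pilot whose tests are all exploratory, and the by-subject listings keep the excluded data.
- A separate Kinesia-360 set is not literally the protocol's definition, which is one FAS based on any efficacy measurement.

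None of this removes the mismatch between the two FAS rules, its absence from SAP 3.9, or the lack of a stated population for the days-of-use summary.

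**Conclusion.** The point holds within limits. SAP 3.5.3 is narrower than protocol 12.1, the change is undeclared, and on the SAP's wording it removes valid device data from the Kinesia-360 change and days-of-use summaries for Experimental Group subjects with no qualifying Visit 2 or Early Withdrawal value.

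The size is probably small. With 1 to 4 of 20 lost after Week 4, scheduled-minimum use is overstated by about 1-4%. About 14% is reached only if four subjects stop after Week 2. These figures assume the loss rate and wear at exactly the scheduled minimum; optional use would change them. The effect on motor scores cannot be signed or sized from the documents.

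The UPDRS Part III and Kinesia-ONE ANCOVAs are not in question here: each needs a Visit 2 or mapped Early Withdrawal value in any case. This is an inexpensive improvement to descriptive tables and does not threaten those comparisons.

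**What to change.** - In SAP 8.2.1, summarise Kinesia-360 changes for all Experimental Group subjects with a Kinesia-360 Baseline and at least one post-Baseline Kinesia-360 week, whether or not they have a Visit 2 value.
- Summarise days of use for all Experimental Group subjects given a device.
- In SAP 3.5.3, say whether a Neupro dose recorded outside a visit can count as a Visit 2 value.
- Leave the set for the UPDRS Part III and Kinesia-ONE ANCOVAs unchanged. This also avoids admitting subjects to a group comparison through a measure that only one arm has.
- In SAP 3.9, declare both the narrowed FAS and the separate Kinesia-360 set.

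The cost is SAP wording and one population flag, with no new data. The n of the Kinesia-360 tables may differ from the FAS n and needs a footnote.
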